2 PRIMARY OBJECTIVE

1. To determine the safety and tolerability of the use autologous volar fibroblasts to reprogram non-volar to KRT9-expressing volar epidermis in human participants.

SECONDARY OBJECTIVES

1. To measure non-invasively for epidermal thickening in sites of injection of volar fibroblasts compared to both non-volar fibroblast injection and vehicle only injection
2. To measure for molecular changes in excised injected skin (for example increases in KRT9).
3. To describe persistence of epidermal thickening in sites of injection of volar fibroblasts over time.
4. To evaluate the safety and efficacy of an intermittent, serial dosing regimen of the autologous volar fibroblasts.
5. To evaluate the efficacy of superficial wounding with a curette at the injection sites.

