5.2.5 GRAFT MONITORING AND REMOVAL

Dependent upon participant response, as many as six monitoring visits will be conducted to evaluate skin thickness and adverse events (see study Schemas, page 3-4). As per the pre-IND discussion with FDA, persistence of any thickening response is of particular interest. In order to assess this, we will divide the subjects such that there will be 2 groups. The first portion will immediately have graft removal once skin thickness increases in order to assess the molecular features of induction of volar skin, and a 2nd portion of subjects will instead be followed for permanence of effect, and undergo graft removal at the conclusion of 10 months of the study.

The method of dividing the subjects will be as follows. At all monitoring visits all injected sites on all subjects will be measured for epidermal thickness by non-invasive confocal imaging or through the non-invasive measurement of skin induration (as long as those injected sites have not been removed through biopsy). The first three subjects who demonstrate a statistically significant increase of measured epidermal thickness on the volar fibroblast injected side will have their grafts removed during the follow-up visit that the increased thickness determined to be statistically significant.

The means of calculating an increase in epidermal thickness of the volar fibroblast injected site will be through a t-test statistical analysis of 3 sequential readings (within a visit) from the three injection sites (no fibroblasts, non-volar fibroblasts, and volar fibroblasts). For a subject to be designated as an “early graft removal”, he/she should have a statistically significantly elevated epidermal thickness in the volar injected site but not the non-volar or vehicle-only injected sites.

If no subjects show an increase, then all subjects will be followed for epidermal thickness till the end of the study and undergo graft removal at the end of the 10 months. If fewer than 3 subjects are identified before the end of the study to have an increase, then the remainder will undergo graft removal at the end of the study. If more than 3 subjects are identified, then those remaining subjects will be

followed through Visit 8 and undergo graft removal at the end of the 10 month period..

“Early Graft Removal” subjects will skip all remaining graft monitoring visits and instead go directly to suture removal visit.

All subjects will have at least one monitoring visit.

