9.2 ANALYSIS PLAN

The first method of analysis will happen during each participant's graft monitoring visits to determine whether they will be one of three "Early Graft Removal" subjects. Three epidermal thickness measurements will be calculated at each monitoring visit for each injection site. We will analyze this data to determine whether volar fibroblasts caused an increase in epidermal thickness. The means of determining whether an increase is statistically significant will be through a t-test statistical analysis of 3 independent readings from the three injection sites (no fibroblasts, non-volar fibroblasts, and volar fibroblasts). We will consider a p value less than 0.05 as significant. For a subject to be designated as an "early graft removal", he/she should have a statistically significantly elevated epidermal thickness in the volar injected site but not the non-volar or vehicle-only injected sites.

For statistical analysis at the conclusion of the study we will average multiple subject's values. We will perform a student's T-test comparing the values of epidermal thickness between at least 3 non-volar fibroblast injections and 3 volar fibroblast injection to determine a p value for a significant difference. We will consider a p value less than 0.05 as significant. We will do the same for KRT9 mRNA values. As more participants complete the study, we will repeat this calculation until our enrollment goal is met.

Power analysis: With a difference of mean assumed to be 2, standard deviation of all samples to be 0.5, alpha 0.06, power of 0.8 then a sample size of 3 participants will be sufficient and our goal will exceed this.

We will perform repetitive interim data analysis as each participant completes the final time point.

We will also calculate average areas of increased epidermal thickness.

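### The final volar versus non-volar tests do not separate grafts removed early because the volar site tested thick from grafts removed at the end

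*Combined protocol and SAP*

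**What the plan says.** Section 5.2.5 splits subjects by their response. "The first portion will immediately have graft removal once skin thickness increases", to study the molecular features of induction, while "a 2nd portion of subjects will instead be followed for permanence of effect". Early removal goes to the first three subjects whose volar site, but neither other site, is significantly raised on a t-test of three readings per site within a visit. Their grafts come out at that visit and they have no further monitoring.

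Section 9.2 then states: "For statistical analysis at the conclusion of the study we will average multiple subject's values". The test is a Student's t-test "comparing the values of epidermal thickness between at least 3 non-volar fibroblast injections and 3 volar fibroblast injection". KRT9 mRNA is handled the same way, and the calculation is repeated as participants complete until enrolment is full. No analysis visit, last-value rule or removal group is named. Secondary objective 3 is separate: "To describe persistence of epidermal thickening in sites of injection of volar fibroblasts over time".

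Two inputs conflict. The share removed early is half of participants in the Abstract but three subjects in section 5.2.5 and the schedule footnotes. Final removal is at the end of 10 months in section 5.2.5 but on study Day 182 in section 5.2.5.6 and both schedules.

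**The concern.** The two groups differ in when they are measured and in why. An early-removed subject's last OCT value exists because the volar site read high that day, and no end-of-follow-up value can exist for that subject. A single average over last values therefore uses the same readings to select and to test, and it leans toward an effect.

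KRT9 and histology come only from excised tissue, so each subject contributes one time point. Pooling all subjects combines early tissue, which speaks to induction, with late tissue, which speaks to persistence. The pooled mean answers neither question, although section 5.2.5 formed the groups to answer them separately.

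**Working it through.** **The plan's own figure.** Section 9.2 gives "With a difference of mean assumed to be 2, standard deviation of all samples to be 0.5, alpha 0.06, power of 0.8", and concludes "then a sample size of 3 participants will be sufficient and our goal will exceed this". For a two-sided unpaired t-test the noncentrality is 2 / (0.5 × √(2/n)).
- n = 3: 2 / 0.408 = 4.90 on 4 df, power 96.3% at alpha 0.06 (94.8% at the 0.05 used for the tests).
- n = 2: 2 / 0.5 = 4.00 on 2 df, power 63.0% at alpha 0.06.

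So n = 3 per group reproduces as the smallest size reaching 80%. The calculation takes the three as unselected and measured at a common time.

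**Tissue timing**, taking Day 182 as the end:
- Visit text (monitoring on Days 42 to 154): 182 − 154 = 28 days to 182 − 42 = 140 days.
- Excision row as printed in Appendix I (Days 98 to 154): 28 days to 182 − 98 = 84 days.

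**OCT thickness under a last-value reading.** The documents give no variance components, so the SDs below are assumptions in units of the single-reading SD. Settings: no true effect, 20 subjects, five monitoring visits plus a final visit, three readings per site. Removal is triggered when the volar site exceeds both others at two-sided p < 0.05 and non-volar does not exceed vehicle. The first three triggered subjects contribute the trigger-visit value and the rest the final value. The final test is unpaired at 0.05, so the nominal volar-direction rate is 2.5%. There were 4,000 runs per row; the simulation standard error at 2.5% is √(0.025 × 0.975 / 4000) = 0.25 points.

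| Stable site SD; visit-to-visit SD | Mean number removed early | Bias, volar minus non-volar | Volar-direction false positives |
|---|---|---|---|
| 0; 0 | 0.39 | +0.03 | 3.7% |
| 1; 0 | 2.06 | +0.08 | 3.9% |
| 1; 1 | 2.82 | +0.28 | 7.5% |
| 0; 1 | 2.57 | +0.37 | 13.8% |
| 2; 2 | 2.99 | +0.43 | 5.2% |

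Hand check of row 1: 0.394 removed early × a mean excess of 1.636, divided by 20, gives 0.032.

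Further runs under the same reading:
- Paired test: bias +0.04 to +0.44 and false positives 2.5–9.8% in one set; 3.1–10.5% in another. Pairing alone does not remove the bias.
- Unpaired test with between-subject SD 1, site variation only and staggered accrual: bias +0.03 to +0.08, false positives 0–1.7%.
- 100 subjects with three early removals (site and visit SD 1): +0.07 and 5.3%.
- Up to half of 20 removed early, as in the Abstract: +0.03 to +1.15 and 3.5–24%.
- A common visit measured in everyone before any removal: 2.1–2.9%, with no bias by construction.

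**Fading effect** (site and visit SD 1). If a true effect falls from 2 to 0 by the final visit, the pooled estimate is +0.48 with three early removals, when the end-of-study effect is 0. This combines time mixing with selection, since the same setting gives +0.28 with no effect at all.

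**Which model corrects it.** With a subject effect only, the final-visit contrast was biased by −0.19 to −0.51 whenever sites differ. Adding a site-within-subject random effect brought the bias to 0.04 or less in absolute value.

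**The case against.** The strongest reply is that no sentence says trigger-visit and end-of-study OCT values will be combined. All subjects are scheduled for OCT at shared visits before removal, so a common-visit analysis would fit section 9.2 as written. That stands: the OCT bias is conditional on a last-value reading. But section 9.2 does not exclude that reading, and for KRT9 and histology no common visit is available.

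The reply also says that the effect is modest, that thickness and KRT9 are secondary outcomes in a feasibility study, and that section 5.2.5 already gives the groups different purposes. The first two points hold for three of 20 in several settings, and they limit the priority. The third does not help, because section 9.2 does not carry the split into the test.

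Two stronger readings are tempting, and the documents support neither.
- A reader might infer that the first 3-versus-3 look is almost certain to mislead. If a look consisted solely of the three early-removed subjects, false significance would run at 57–96% across the settings tried with removal possible from the first monitoring visit. But section 9.2 ties looks to each participant's final time point, and section 5.2.7 brings early-removed subjects back at Day 273 like everyone else. Completion should then follow enrolment order. With six-month staggered accrual, the first three enrolled were exactly the three early removals in 0–0.5% of null trials.
- A reader might infer that KRT9 is itself selected on its outcome. The trigger acts on OCT readings, and OCT reading error cannot bias RT-PCR. Selection reaches KRT9 only as far as KRT9 correlates with thickness.

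**Conclusion.** The concern holds in a limited form and should be corrected. For KRT9 and histology, pooling all subjects necessarily mixes tissue 28 to 140 days apart by the visit text, or 28 to 84 by the printed excision row. That follows from the schedule if Day 182 is the end, and needs no variance assumption.

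For OCT thickness, using last values biases the contrast toward a volar effect by about 0.03 to 0.44 reading SDs with three of 20 removed early. Volar-direction false positives run from nominal to roughly 10–14%, depending on visit-to-visit variation and the test. There is little or no inflation in the unpaired test when between-subject variance is large. These sizes rest on assumed variance components. They shrink with three of 100 and grow if half may be removed early.

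**What to change.** 1. Analyse OCT within subject. Either compare volar with non-volar at one prespecified visit measured in all subjects before any removal, or fit a repeated-measures model to all readings up to and including the removal visit. The model needs site-by-visit fixed effects, random effects for both subject and site within subject, and the contrast at a named visit. Include all three sites, since the trigger uses them. Removal depends on observed readings, so a likelihood model can handle it if the covariance is right; a subject effect alone is not enough. The single early visit is simpler but says nothing about persistence.
2. Report KRT9 and histology within subject, separately for early-removed tissue (labelled as selected) and end-of-follow-up tissue.
3. State that no test will be run on a set made only of early-removed subjects.
4. Reconcile the passages on the share removed early (half in the Abstract, three in section 5.2.5) and on final removal (10 months in section 5.2.5, Day 182 in section 5.2.5.6).

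Items 1 to 3 cost SAP wording, slightly more analysis and smaller numbers in each KRT9 summary. They add no visit or procedure.

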3 BACKGROUND

[figure not shown]

Figure 1: Properties of Volar versus Non-Volar Skin. Note **Keratin 9** expression is limited to thick volar skin.

(Adapted from Rinn et al[1])

Solution: Convert stump skin to weight-bearing volar (i.e. palmoplantar) skin

The goal of this proposal is to make the placement of a prosthetic at a stump site analogous to the placement of a shoe on a foot, for example. We hope to achieve the rarity of skin break-down at the soles of our feet for stump sites in amputation victims. Therefore we propose to convert stump

skin to volar type skin with its attendant friction-resistant, irritant-resistant and weight bearing properties.

Properties of Volar Skin (Figure 1)

Volar skin, found at our palms and soles, has many distinguishing features adapted for their location as frequent points of interface with our environment. The primary feature of volar skin is the thick stratum corneum—the very top layer of skin which consists of dead keratinocytes which are cross-linked to form a strong water-impermeable layer. This stratum corneum is approximately 10 times as thick as in other parts of the skin. The thickness of this layer allows for more even distribution of weight across volar skin, resistance to friction, resistance to injury and impermeability to irritants and allergens.

These physical differences are reflected in different proteins which are expressed in volar skin (see Preliminary Studies). The most well studied one is Keratin 9. This structural molecule is unique to volar skin and provides tensile strength to cells (Figure 1).

Fibroblasts: Candidate Therapy to Convert Non-Volar to Volar Skin

The skin is made of two parts, the top epidermis and the bottom dermis. The predominant cell in the epidermis is the keratinocyte. The predominant cell in the dermis is the fibroblast. Fibroblasts have important functions in controlling tissue identity. Evidence for this comes from both animal studies and human studies.

The primary innovation of this investigation is to clinically apply established concepts in developmental biology of the mesenchymal (dermal fibroblast) control of epithelial (keratinocyte) function. Early experiments swapping chicken and duck epithelium and mesenchyme established that mesenchyme controls epidermal identity[3]. We hope to translate this fundamental concept to help improve the quality of life for amputation victims.

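### KRT9 mRNA inherits the thickness t-test with no stated log (delta-Ct) scale and no pairing; if raw expression is analysed, induction can be missed at the small sample sizes where testing starts

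*Combined protocol and SAP*

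**What the plan says.** Section 9.2 (Analysis Plan) describes the final analysis for thickness first: "we will average multiple subject's values", then a Student's t-test "between at least 3 non-volar fibroblast injections and 3 volar fibroblast injection to determine a p value for a significant difference". The threshold is "We will consider a p value less than 0.05 as significant". KRT9 follows in one sentence: "We will do the same for KRT9 mRNA values". The calculation is repeated as further participants complete.

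The only power statement, also in 9.2, concludes "alpha 0.06, power of 0.8 then a sample size of 3 participants will be sufficient". Its effect-size inputs are a mean difference of 2 and one common SD of 0.5. It has no units and does not name the endpoint. Section 9.1 supports the sample size for KRT9 by pointing to Figure 8, whose caption concerns optical imaging of thickness. No KRT9 mean, fold change or SD appears in the text.

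Section 9.2.2 makes a rise in KRT9, by RT-PCR, western blot or immunohistochemistry, a secondary outcome. The Background says of KRT9: "This structural molecule is unique to volar skin and provides tensile strength to cells". The Abstract describes volar and non-volar cells injected into paired areas of the same participant. Nowhere is there a log or delta-Ct scale, a reference gene, or a rule for values below detection.

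**The concern.** A t-test that suits thickness need not suit mRNA. RT-PCR expression usually varies by fold, so on the raw scale the spread grows with the mean. The protocol also regards KRT9 as specific to volar skin, so one would expect low values at non-volar sites and much higher values at any converted site. A single common SD is then implausible for raw values. One strong responder raises the mean difference and the SD together, and the t statistic can stay small even when every participant shows induction. On a log scale, such as delta-Ct, this problem largely goes away.

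The test is also not stated to be paired, so differences between people may be left in the error term.

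KRT9 is the marker the protocol itself favours for showing conversion. At stake is failing to detect real induction, with a reported mean that depends on one or two people. Because the scale is left open and the test is rerun as participants complete, the scale could also be settled after results are seen.

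**Working it through.** **1. The plan's own figure.** Inputs from Section 9.2: difference 2, SD 0.5, alpha 0.06, power 0.80. For a two-sample t-test, df = 2n − 2 and noncentrality = (2/0.5)·√(n/2).
- n=2 per group: noncentrality 4.00, df 2, power 63.0%.
- n=3 per group: noncentrality 4.90, df 4, power 96.3% (94.8% at alpha 0.05).

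So 3 is the smallest n with at least 80% power, and the stated figure reproduces with a constant SD. What it means for KRT9 depends on the missing units (step 5).

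**2. Model for KRT9 (assumptions; the documents give no values).** For each participant, log2 non-volar = b + e1 and log2 volar = b + 2 + e2, which is a 4-fold induction. The person effect b has SD 1. Each e has SD d/√2, so the within-person difference has SD d, taken as 1, 1.5 and 2. The implied correlation between sites is 1/(1 + d²/2) = 0.67, 0.47 and 0.33. There is no detection floor in this model.

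**3. Power by simulation**, two-sided 0.05, in percent (200,000 trials per cell; 40,000 for n=3):

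| d | n | log2 paired | log2 unpaired | raw paired | raw unpaired |
|---|---|---|---|---|---|
| 1 | 3 | 47 | 35 | 15 | 22 |
| 1 | 6 | 97.1 | 79.9 | 62.4 | 55.5 |
| 1 | 10 | 100.0 | 98.6 | 91.1 | 83.6 |
| 1 | 20 | 100.0 | 100.0 | 99.4 | 98.4 |
| 1.5 | 3 | 27 | 24 | 9 | 14 |
| 1.5 | 6 | 74.1 | 59.7 | 34.6 | 34.8 |
| 1.5 | 10 | 96.2 | 88.8 | 68.0 | 62.1 |
| 1.5 | 20 | 100.0 | 99.9 | 94.5 | 91.5 |
| 2 | 3 | 18 | 18 | 6 | 9 |
| 2 | 6 | 50.8 | 43.5 | 18.3 | 20.9 |
| 2 | 10 | 80.3 | 71.9 | 41.6 | 40.2 |
| 2 | 20 | 98.8 | 97.3 | 77.4 | 73.8 |

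Loss at n=20, paired log2 minus raw paired and raw unpaired: 0.6 and 1.6 points at d=1; 5.5 and 8.5 at d=1.5; 21.4 and 25.0 at d=2.

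**4. Scale and pairing separated.** At d=1.5, n=6, going from raw unpaired to log2 unpaired adds 59.7 − 34.8 = 24.9 points. Adding pairing gives a further 74.1 − 59.7 = 14.4 points.

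**5. The plan's own numbers, given units** (unpaired test, independent sites, raw versus log):
- Read as PCR cycles (4-fold, SD 0.5 cycle): 82.8% versus 94.6% at n=3; both at least 99.9% from n=6.
- Read as raw means 1 and 3 with a constant coefficient of variation of 0.5: 44.5% versus 57.4% at n=3; 90% versus 95% at n=6; both about 100% at n=20.

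**6. Null case** (no induction). The paired log2 test rejects in about 5% of trials and the raw tests in 4% or fewer. This is for a single test; the repeated looks are a separate matter.

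**7. Signed-rank check.** The smallest two-sided p is 2/2ⁿ: 0.25 at n=3, 0.0625 at n=5, 0.031 at n=6.

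**The case against.** The strongest reply is that 9.2 fixes the test but not the scale. Delta-Ct values are already logarithmic, and a t-test on them is largely what is wanted; the difference of 2 with one SD of 0.5 could even be PCR cycles. This stands. A reader might infer that the plan commits to raw expression; the documents do not say so. What is established is an unstated scale.

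A reader might also infer that control values sit at the assay floor. The Background supports low values, but no control level, detection limit or distribution is given, and the main simulation has no floor.

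A third tempting reading is that much of the power is lost in the final analysis. Section 4.1 plans 20 participants in Phase One and up to 80 more in Phase Two. At n=20 the loss is small if variability is modest. With 10-fold rather than 4-fold induction, raw power at n=20 is about 93% even at SD 2. The large losses belong to the small samples. Those are still in the plan, since testing begins with "at least 3 non-volar fibroblast injections and 3 volar fibroblast injection".

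Pairing is not free either. If the two sites were uncorrelated, a paired log test with 3 pairs would do worse than an unpaired one (35% versus 57% for 10-fold induction with a natural-log SD of 1.0). By n=10 the difference is negligible (99.6% versus 99.8%).

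Finally, this is a feasibility study with tolerability as its primary outcome (9.2.1). KRT9 is secondary, can also be shown by other assays, and a conservative test does not create false claims of induction. That limits the consequence but does not remove the gap.

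**Conclusion.** The concern holds in a limited form. Section 9.2 carries the thickness t-test over to KRT9 mRNA without a stated scale, without stated pairing and without a rule for undetected values. If raw expression is analysed, real induction may be missed at small n. Under the assumed 4-fold induction and between-person SD of 1 log2 unit, the paired log2 test gains at n=6 and n=10 across the whole range of SDs tried. At n=20 the gain matters only when within-person variability is high. About a third of the gain over the raw unpaired test at SD 1.5, n=6 comes from pairing (14 of 39 points).

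The sizes rest on assumed fold change and variances, because the documents supply none. The direction follows for any fold-type variation analysed raw. If delta-Ct is already intended, what remains is to say so, pair the sites and state the rule for undetected values.

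**What to change.** In 9.2, replace the one-sentence KRT9 instruction with:

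- **Analysis.** KRT9 mRNA is analysed as the within-participant volar minus non-volar difference in normalised log2 expression (delta-Ct against a named reference gene, signed so that higher means more expression), by a paired t-test. It is reported as a geometric mean fold change with 95% interval.
- **Undetected values.** Treat them as below the limit. Report the number detected for each site type. Give the fold change as a lower bound, or with a sensitivity range over the imputed cycle; one fixed last-cycle value would make the estimate depend on an arbitrary number.
- **Check.** When any value is undetected, add a signed-rank or sign test, noting that a two-sided signed-rank test cannot reach p<0.05 with fewer than 6 pairs.

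The cost is a few sentences and no new samples or assays. The result becomes a fold change rather than an arithmetic mean difference, and with only 3 pairs the paired test has 2 degrees of freedom instead of 4.
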